5.4. Other Efficacy Variable(s)

5.4.1. Definition

Analysis of the following efficacy endpoints are considered exploratory:

- Time to symptomatic deep vein thrombosis (DVT)

- Time to symptomatic pulmonary embolism (PE)

5.4.2. Analysis Methods

The number of symptomatic DVT and PE events is expected to be small. Due to the exploratory nature of the analysis and consideration of the type I and type II errors, no statistical testing will be conducted for these 2 exploratory endpoints. However, the size of the treatment effects, including corresponding 95% CI, of time to DVT and time to PE will be estimated using a Cox proportional hazards model with treatment as the only covariate. Because of the small number of events expected, the Cox model is not stratified.

In order to understand the impact of strokes, the modified Rankin score will be collected within 6-18 weeks following a stroke or at the end of study, whichever occurs first. The distribution, (i.e., frequency and percentage), of the modified Rankin score will be tabulated for stroke events.

5.5. Additional Efficacy Analyses

For all primary, secondary and other efficacy outcome events discussed above, the number of subjects with these events will be tabulated for the following analysis sets:

- Off-treatment observation period for subjects who permanently discontinue study drug for any reason prior to GTED
- Off-treatment observation period for subjects who complete the double-blind treatment period and have the EOS visit (Office/Phone)
- Off-treatment observation period for the Safety population.
- Day 3 to Day 30 after the last dose observation period for subjects who permanently discontinue study drug for any reason prior to GTED
- Day 3 to Day 30 after the last dose observation period for subjects who complete the double-blind treatment period and have the EOS visit (Office/Phone)
- Day 3 to Day 30 after the last dose observation period for the Safety population.

6. SAFETY

6.1. Bleeding Events

The principal safety endpoint for this study is the composite of fatal bleeding or bleeding into a critical space with a potential for permanent disability. A fatal bleeding event is one in which the subject dies within 7 days of a bleeding event requiring hospitalization or ISTH major bleeding. Fatal bleeding events will include those that meet the criteria in the following three exclusive categories:

- Category 1: Any ISTH major bleeding event considered to be the primary cause of death by the investigator (i.e., Question 5 on the BLEED page of the eCRF is answered 'Yes'),
or

- Category 2: Any ISTH major bleeding event not considered to be the primary cause of death by the investigator (i.e., Question 5 on the BLEED page of the eCRF is answered as 'No') but results in death within 7 days, or
- Category 3: Any bleeding event that results in a hospital stay and death within 7 days (i.e., death and either Question 6 or 8 on the BLEED page of the eCRF is answered 'Yes')

The following organs are considered critical:

- Intracranial
 - Intraparenchymal
 - Intraventricular
 - Subdural Hemorrhage
 - Subdural
 - Epidural
- Intra-spinal
- Intraocular—other than sub-conjunctival
 - Vitreous
 - Retinal
- Pericardial
- Intra-articular
- Intramuscular with compartment syndrome
- Retroperitoneal

Similar to the analyses planned for the primary efficacy endpoint as described above, time to the first occurrence of the principal safety endpoint will be compared using a log-rank test and a Cox proportional hazards ratio model with treatment as the only covariate. Both the log-rank test and Cox proportional hazards models are stratified by region. A plot of cumulative event rate derived by Kaplan-Meier estimate will be provided to show event rate and treatment effect by time. The analyses will be conducted based on analysis set defined by the on-treatment observation period and the safety subject population. Subjects will be analyzed according to study drug assigned. Significance level is always at the nominal level of 0.05 for safety analyses. There will be no adjustment for multiplicity. The same analysis will be repeated for the post-first dose observation period and the safety subject population.

Time to the first occurrence of following bleeding events will be analyzed using the same method.

- Bleeding requiring hospitalization
- ISTH major bleeding

The number of subjects with the above safety outcomes will be tabulated for the following observation periods and analysis sets:

- Off-treatment observation period for subjects who permanently discontinue study drug for any reason prior to GTED

- Off-treatment observation period for subjects who complete the double-blind treatment period and have the EOS visit (Office/Phone)
- Off-treatment observation period for the Safety population.
- Day 3 to Day 30 after the last dose observation period for subjects who permanently discontinue study drug for any reason prior to GTED
- Day 3 to Day 30 after the last dose observation period for subjects who complete the double-blind treatment period and are have the EOS visit (Office/Phone)
- Day 3 to Day 30 after the last dose observation period for the Safety population.

The number of the subjects with other reported bleeding events will be summarized by treatment group and bleeding site. For Japan subjects only, summary statistics will be provided for non-major clinically relevant bleeding events and minimal bleeding events.

6.2. Other Adverse Events

Because the safety profile of rivaroxaban has been well established in previous large and extensive trials, this study will collect limited AE data (see Section 12 of the study protocol for AE data to be collected). For AEs that are collected, the verbatim terms reported in the eCRF by investigators to identify adverse events will be coded using the Medical Dictionary for Regulatory Activities (MedDRA). For each MedDRA preferred term, the percentage of subjects who experience at least 1 occurrence of the given event will be summarized by treatment group. The difference between treatments in the percentage will be provided. If an AE is reported by 4 or more subjects in the entire safety population, a 95% CI for the difference will also be provided. The 95% CI is calculated based on the normal approximation of binomial data without continuity correction. This is corresponding to the approach for Tier 2 events (signal detection among common events) proposed by [Crowe et al \(2009\)](#). Additional summaries, listings, or subject narratives may be provided, as appropriate.

AEs reported by investigators will be summarized based on the analysis set defined by the on-treatment observation period and separately by the post-first dose of study drug observation period and the safety subject population.

Based on specific safety reporting requirements from the Pharmaceuticals and Medical Devices Agency, AE data from Japan may not be directly comparable with those collected from non-Japan sites. Therefore, the AE data from Japan sites may be summarized separately from AE data from non-Japan sites in the respective reported safety tables.

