1.4. Sample Size Justification

This is an event driven study. The study was designed to observe occurrences of the primary efficacy event in 984 unique randomized subjects, on or before the GTED, to have 90% power to detect a 20% relative risk reduction (RRR, defined as one minus hazard ratio) in the composite of ACM, MI, or stroke at 5%, 2-sided significance level. A total of approximately 5000 subjects will be randomly assigned to either the rivaroxaban arm or the placebo arm in a 1:1 ratio.

The above sample size calculation was estimated based on the following additional assumptions:

- Event rate for the composite endpoint in the placebo arm: 19%/year
- Permanent premature treatment discontinuation rate: 10%/year
- Lost-to-follow-up: 1%/year
- Duration of enrollment period: 24 months (see [Attachment 1](#) for distribution of enrollment by month)
- Duration of study (from first subject randomized to last EOS visit): 31 months

The assumptions of RRR and event rate were based on observations from HF subjects in the ATLAS ACS 2 TIMI 51 study. Observed data from HF subjects of ATLAS ACS 2 TIMI 51 study are summarized in the table below (Source: Adhoc analyses on file).

	Event Rate (%/patient-year)		Hazard Ratio (95% CI)
	Rivaroxaban 2.5 mg bid	Placebo	
HF Subjects	(N=562)	(N=558)	
ACM/MI/Stroke	9.43	16.64	0.57 (0.41, 0.79)
ACM	3.54	8.31	0.43 (0.26, 0.70)
MI	5.73	8.47	0.67 (0.44, 1.03)
Stroke	1.08	1.60	0.69 (0.26, 1.81)

Based on historical data, the mortality rate in this study was expected to be higher, and the rate of MI was expected to be lower, than the observed corresponding rates in ATLAS ACS 2 TIMI 51 study. After adjusting for differences in these event rates, an event rate of 19%/year for the composite endpoint in the placebo group was used in the sample size calculation. Event rates in the placebo group for the components ACM, MI, and stroke are expected to be approximately 14%, 4%, and 2% per year, respectively.

Although the RRR observed in ATLAS ACS 2 TIMI 51 study was 43% (95% CI [21%, 59%]), a RRR of 20% was assumed in the sample size calculation. The lower RRR close to the lower bound of the 95% CI was used to be conservative because the subject population in the current study was considered different from the HF subgroup in ATLAS ACS 2 TIMI 51.

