2.3. Analysis Sets

The definition of an analysis data set consists of these 2 elements: 1) *subject population*, which specifies which subjects will be included in an analysis; and 2) *observation period*, which specifies the time window within which data will be included in an analysis. Key subject populations and observation periods are defined below.

Subject Populations

Intention-to-treat (ITT) population: This subject population consists of all randomized unique subjects who have a signed valid informed consent.

Per-Protocol (PP) population: This population is a subset of the ITT population, consisting of subjects who do not have a major protocol deviation in the following categories (see FRM-15949 for the specific major protocol deviations that are exclusions from the PP population and identification/review process):

- Entered but did not satisfy criteria
- Received a disallowed concomitant treatment

- Received wrong treatment or incorrect dose (includes subjects with treatment compliance rate < 75% calculated according to a formula described in Section 4.3)
- Developed withdrawal criteria but not withdrawn
- Other (as appropriate)

If appropriate, additional ad hoc exclusion criteria for the PP population may be applied. Subjects to be excluded from the PP population will be determined and documented prior to database lock, except for those who are excluded from PP due to taking the wrong treatment . Because unblinded data are needed to determine whether a subject has taken incorrect study drug, subjects excluded from the PP population due to taking any incorrect study drug will be determined after data unblinding, according to the pre-specified rule.

Safety population: This population is a subset of the ITT population, consisting of subjects who receive at least one dose of study drug.

Observation periods

Up-to-GTED: this observation period includes all data from randomization to the GTED, inclusively. For time to event analyses, subjects who do not have events to be analyzed on or before the GTED will be censored on the GTED or the last contact date whichever occurs first.

On-treatment: this observation period includes data from the first dose of study drug to 2 days after the last dose of the study drug, inclusively. For time to survival event analyses, subjects who do not have events to be analyzed for this period will be censored on the last day of the period (last dose + 2) or the last contact date whichever occurs first.

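### The normal-approximation interval for adverse-event differences (SAP Section 6.2) sets the upper limit too low for sparse one-sided splits, by about 23% at 4 versus 0

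*SAP*

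**What the plan says.** SAP Section 6.2 tabulates each MedDRA preferred term by arm, with the difference in percentages. The interval is triggered by a count over both arms: "If an AE is reported by 4 or more subjects in the entire safety population", then "a 95% CI for the difference will also be provided". The method is stated: "The 95% CI is calculated based on the normal approximation of binomial data without continuity correction". The section places it within a published tier scheme: "This is corresponding to the approach for Tier 2 events (signal detection among common events".

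It names no other method for small counts, does not say whether the variance is pooled, and gives no rule for reading an interval that excludes zero. Section 6.1 says of safety analyses: "Significance level is always at the nominal level of 0.05 for safety analyses", with no multiplicity adjustment.

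**The concern.** The method is described as one for common events, yet it starts at 4 subjects among about 5,000, which is 0.08%. The normal approximation estimates each arm's variance from its observed proportion. An arm with no events gets a variance of zero, as if its risk were known to be exactly zero, and the other arm's variance rests on a handful of events.

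For a rare term seen in only one arm, the useful part of the interval is the upper limit, because it says how much harm the data still allow. A limit that is too low makes the table look more reassuring than the data justify. Section 6.2 collects only limited adverse-event data by design, so readers have little else with which to correct that impression.

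**Working it through.** **Inputs.** Threshold of 4 in total, two-sided 95% level and normal approximation without continuity correction: Section 6.2. Arm size: Section 1.4, "A total of approximately 5000 subjects will be randomly assigned to either the rivaroxaban arm or the placebo arm in a 1:1 ratio", so about 2,500 per arm. The safety population is slightly smaller, "consisting of subjects who receive at least one dose of study drug" (Section 2.3), so 2,500 is an assumption. Unpooled variance is also an assumption. The SAP states no figure on this point, so there is none to reproduce; its rule was applied as written.

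**Step 1: the SAP interval at 4 versus 0.**
d ± 1.96·√[p₁(1−p₁)/n₁ + p₂(1−p₂)/n₂], with p₁ = 4/2,500 = 0.0016 and p₂ = 0.
Standard error = √(0.0016 × 0.9984 / 2,500) = 0.000799; 1.96 × 0.000799 = 0.001567.
Interval: 0.000033 to 0.003167, or 0.3 to 31.7 per 10,000.

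**Step 2: the Newcombe interval at the same split.** It combines the single-arm Wilson limits (l, u):
lower = d − √[(p₁−l₁)² + (u₂−p₂)²]; upper = d + √[(u₁−p₁)² + (p₂−l₂)²].
Wilson limits are 0.000622 to 0.004107 for 4/2,500 and 0 to 0.001534 for 0/2,500.
Lower = 0.0016 − √(0.000978² + 0.001534²) = −0.000219. Upper = 0.004107.
Interval: −2.2 to 41.1 per 10,000.

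**Step 3: size of the shortfall in the upper limit (per 10,000).**

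| Split | SAP method | Newcombe | Shortfall |
|---|---|---|---|
| 4 vs 0 | 31.7 | 41.1 | 1 − 31.7/41.1 = 23% |
| 5 vs 0 | 37.5 | 46.7 | 20% |
| 6 vs 0 | 43.2 | 52.3 | 17% |

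At 4 versus 0, Miettinen-Nurminen also gives 41.1, and the exact (Clopper-Pearson) upper limit for 4/2,500 alone is 40.9.

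A direct check: if the true risks were 31.7 per 10,000 and zero, about 7.9 events would be expected in 2,500 subjects, and 4 or fewer would still occur with probability 10.4%. A 95% upper limit should leave 2.5%. At the Newcombe limit the probability is 2.4%.

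**Step 4: coverage among reported terms** (exact binomial, given a total of at least 4, equal risk).

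| Expected events per arm | SAP method | Newcombe |
|---|---|---|
| 1 | 90.2% | 98.1% |
| 2 | 92.7% | 97.0% |
| 3 | 94.5% | – |
| 5 | 95.6% | – |

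With unequal risks of 8 and 2 expected events, the SAP upper limit falls below the true excess 4.2% of the time and Newcombe's 1.5%, against a nominal 2.5%.

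**Step 5: exclusion of zero.** With x versus 0 and unpooled variance, the lower limit is above zero when x/(1 − x/n) > 1.96² = 3.84. This holds for x = 4 at any arm size. At 2,500 per arm, 3 versus 0 does not exclude zero (−1.6 to 25.6 per 10,000). Fisher's p at 4 versus 0 is 0.125. With 1:1 arms, equal risk and a total of exactly 4, the split is 4-0 or 0-4 with probability 2 × 0.5⁴ = 12.5%; Newcombe excludes zero in neither case. At totals 5 to 15 the two methods exclude zero equally often (for example 6.25% at 5, 3.1% at 6, 7.0% at 8). Under equal risk, missing the true value is the same event as excluding zero, so the low coverage at 1 and 2 expected events comes mainly from the 4-0 split.

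**The case against.** A reader might infer that this table will produce an inflated number of false safety signals. That does not follow. The 12.5% is conditional on a total of exactly 4. Because rarer terms get no interval, the chance that a term with equal risk is both reported and flagged is 1.4% at 1 expected event per arm, 4.1% at 2, 4.7% at 3 and 4.3% at 5, all below 5%. Nor is excluding zero at 4-0 peculiar to this method: Miettinen-Nurminen just does so too (lower limit 0.6 per 10,000). Newcombe itself excludes zero at 5-0, where Fisher's p is about 0.062. The 4-0 exclusion also depends on the variance form: with pooled variance and 4/2,600 versus 0/2,400, the lower limit is slightly negative.

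A reader might also infer that the normal approximation is unusable throughout the sparse range. Coverage of 94.5% to 95.6% at 3 to 5 expected events per arm contradicts that.

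A sensitive flag can be a reasonable choice in a screen, and Newcombe gives up some sensitivity. With 4 versus 0.5 expected events, the chance of flagging the true excess falls from 38% to 26%; with 6 versus 0.5, from 65% to 57%. The plan also discloses its method and cites a convention for it. Whether it departs from that source cannot be judged from the SAP.

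All of this stands, and it limits the weight of the zero-exclusion point. It does not rescue the upper limit: a wish for sensitivity concerns the lower limit and gives no reason to understate the largest excess compatible with the data.

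**Conclusion.** The concern holds in a narrow form. For sparse one-sided splits, the interval fixed in Section 6.2 has error bars that are wrong, chiefly an upper limit 17% to 23% too low when 4 to 6 events fall in one arm and none in the other. Coverage among reported terms is below nominal at 1 to 2 expected events per arm and close to nominal from about 3. Exclusion of zero at 4-0 is a secondary point.

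The figures assume 2,500 per arm and unpooled variance. The consequence is small: Section 6.2 is descriptive and attaches no decision to these intervals. The principal safety endpoint, bleeding requiring hospitalization and ISTH major bleeding are analysed by stratified log-rank and Cox methods in Section 6.1, which this does not touch. No primary conclusion depends on it. It is a desirable correction, not a necessary one.

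**What to change.** In Section 6.2, replace the normal approximation by a score-based interval for all adverse-event risk differences, and keep the 4-subject reporting rule. The Newcombe hybrid-score interval is the suggested choice. Miettinen-Nurminen corrects the upper limit equally well and suits a team that prefers to keep the more sensitive flag at 4-0.

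The cost is one sentence and a standard software option, with no new data. Intervals for rare terms become slightly wider, and those for common terms barely change. With Newcombe there is also some loss of screening sensitivity at the smallest counts, as quantified above; the team should accept that knowingly.

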6.3. Clinical Laboratory Tests

Because the safety profile of rivaroxaban has been well established in previous trials, this study will not collect laboratory data during the study other than D-dimer at Week 4 (10% of subjects) and hemoglobin at Week 12 (up to Week 24). Complete D-dimer data will not be available until after the database lock. There is no plan to analyze laboratory data other than a descriptive summary of the hemoglobin and D-dimer data. Local lab data may be discussed in subject narratives as appropriate.

Change from baseline in Week 4 D-dimer, in the 10% of subjects from whom Week 4 D-dimer values will be collected, will be summarized by treatment group. A similar approach will be used to summarize the hemoglobin data. Mean, standard deviation, median, inter-quartile range, and range will be reported.

6.4. Vital Signs and Physical Examination Findings

Targeted medical history and vital signs are obtained at baseline only and summarized as baseline characteristics. Physical examinations are not required as part of study procedures. Available data may be discussed in subject narratives.

7. Benefit/Risk Assessment

The section below describes several key elements for benefit-risk assessment, including 1) quantification method for benefits and risks, 2) efficacy and safety outcomes included in the evaluation, 3) analysis population and observation period, and 4) reporting format of the results.

The benefit-risk analyses described here are primarily intended to structure an integrated evaluation of the key benefits and risks in the study. They are complementary to other efficacy and safety analyses described elsewhere in this document. The overall benefit-risk profile of the study drug will be interpreted in consideration of the analyses described here and the totality of the data.

Quantification Methods for Measuring Benefits and Risks

As noted in previous sections, the treatment RRRs for efficacy and safety will be assessed using hazard ratios (Cox proportional hazards model). Because of difference in background event rate across different types of outcome events, a preferred metric used to evaluate treatment difference for benefit/risk assessment purpose is absolute risk differences. For the current benefit-risk assessment, the treatment comparison of rivaroxaban vs. placebo will be evaluated based on the excess number of events between treatments, including events intended to be reduced (benefits) and events that may be caused (risks). The excess number of events is defined as the difference in event rates times a hypothetical population size (e.g., 10,000 patients or person-years). The event rate will be calculated based on the time-to-first-event using the following approaches:

- Person-year rate, expressed as number of events per 100 person-years exposure time
- Kaplan-Meier Product-Limit estimates of cumulative event rates at 1-year*

In addition, number-needed-to-treat to benefit (NNT) or harm (NNH) also will be used to quantify benefits and risks of the treatment, respectively, which are calculated as the reciprocal of the differences in corresponding event rates.

*Because the duration of the trial is longer than anticipated, Kaplan-Meier Product-Limit estimates of cumulative event rates at 2-years and 3-years may be explored.

Efficacy and Safety Outcomes for Benefit-Risk Evaluation

The efficacy and safety outcomes that will be included in benefit-risk evaluation are generally consistent with those specified in the efficacy and safety sections of this document, with some minor modifications as noted below. The primary efficacy outcome is the composite of ACM, MI, or stroke, while the principal safety outcome is the composite of fatal bleeding or bleeding into a critical space (intracranial, intraspinal [vitreous or retinal], pericardial, intraocular-other than sub-conjunctival, intra-articular, retroperitoneal, intramuscular with compartment syndrome, retroperitoneal) with a potential for permanent disability. Importantly, for the benefit-risk calculations, fatal bleeding and hemorrhagic stroke would be counted in both the benefit and risk categories (e.g., fatal bleeding will be part of ACM, while hemorrhagic stroke will be part of stroke). Therefore, to avoid double-counting an event as both a benefit and as a risk, the outcomes for the benefit-risk analysis will be the following:

Benefits

Composite of non-bleeding related death, non-fatal MI, or non-fatal ischemic stroke and each component separately:

- Non-bleeding related death
- Non-fatal MI
- Non-fatal ischemic stroke

As a supporting measure, the composite of non-bleeding related death, MI (fatal, non-fatal) or ischemic stroke (fatal, non-fatal) may also be evaluated.

Risks

Composite of fatal bleeding events, non-fatal intracranial hemorrhage, or other bleeding into a critical space with a potential for permanent disability and each component separately:

- Fatal bleeding events
- Non-fatal intracranial hemorrhage
- Non-intracranial hemorrhage, non-fatal bleeding into a critical space with a potential for permanent disability

The two composite endpoints listed above will serve as the primary comparison of benefits and risks (pairwise comparison), since those events are fatal or are likely to cause irreversible harm (Unger 2009, Beasley 2011) and arguably represent events of similar clinical importance. In addition, components of the composite endpoints and other major efficacy and safety outcomes identified in the protocol will also be evaluated in a similar fashion to support the overall benefit-risk evaluation.

Analysis Population and Observation Period

The primary analysis for benefit-risk evaluation will be based on the analysis set defined by the ITT subject population and the up-to-GTED observation period. However, additional analyses using analysis sets defined by other subject populations and/or observation periods as defined in the protocol or in this SAP may be performed as supporting analyses.

Note that the benefit-risk analyses are not intended for hypothesis testing. Therefore, no multiplicity adjustment will be applied. When 95% CIs for point estimates of the excess number of events are provided as appropriate, nominal statistical significance at the alpha level of 0.05 (2-sided) will be declared if the confidence interval excludes zero.

The benefit-risk assessment will also be explored for the subgroups specified in Section 2.4.

Note that although primary composite endpoints and analysis set are mentioned above, assessment of benefit/risk balance is based on the totality of data. It is unlikely that a clear conclusion can be made based on a comparison of a pair of composite endpoints and/or data from a typical analysis data set. Those primary composite endpoints and primary analysis data set provide a starting point. Results of the analyses do not preclude additional benefit/risk assessment in other endpoints and/or analysis population, and they do not carry more weight than other additional analyses in the overall benefit/risk assessment.

Reporting Format of the Results

To facilitate the comparison and interpretation of the results, data will be presented in one of the following formats as appropriate:

- Table format showing the between-treatment differences in benefits and risks (e.g., excess number of events and NNT or NNH)
- Kaplan-Meier plots depicting between-treatment differences in benefits and risks over time (for the pairwise comparison)
- Forest plots for comparing key benefits and risks (as discussed above), as well as other main efficacy and safety outcomes measures

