The study is revised to observe occurrences of the primary efficacy event in 1,200 unique randomized subjects based on a simulation study performed on available trial data, i.e., longer enrollment period, lower than anticipated primary efficacy event rate, higher than anticipated study drug discontinuation rate:

- Event rate in the placebo arm: approximately 16%/year based on the observed combined event rate at 14%/year (assumed 20% of RRR remains)
- Early permanent study drug discontinuation rate: approximately 13%/year
- Duration of enrollment period: approximately 48 months (projected)

The simulation study estimated that the duration of study may extend to approximately 54 months based on the fact that the original goal of enrolling a total of 5,000 subjects remains

unchanged and all subjects would be observed for approximately 6 months after the last subject is enrolled.

With an effect size of 20% and overall α level of 5% (2-sided), 1,200 primary efficacy events will produce a statistical power of approximately 80%.

An interim analysis will be conducted when primary efficacy events are observed in approximately 600 unique subjects (see Section 3 for more details).

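### Section 7's Kaplan-Meier event rates treat deaths outside the endpoint as censoring, which overstates bleeding and non-fatal event risks in each arm but hardly touches the benefit composite

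*SAP*

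**What the plan says.** SAP Section 7 prefers absolute risk differences. It expresses them as excess events in a hypothetical population (10,000 is the example) and as NNT or NNH, the reciprocals of the rate differences. Time-to-first-event rates come from two approaches. The first is "Person-year rate, expressed as number of events per 100 person-years exposure time". The second is "Kaplan-Meier Product-Limit estimates of cumulative event rates at 1-year", with a footnote that "Kaplan-Meier Product-Limit estimates of cumulative event rates at 2-years and 3-years may be explored". Among the reporting formats are "Kaplan-Meier plots depicting between-treatment differences in benefits and risks over time (for the pairwise comparison").

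The benefit composite is non-bleeding death, non-fatal MI or non-fatal ischemic stroke. The risk composite is fatal bleeding, non-fatal intracranial hemorrhage or other critical-space bleeding. Each component is also reported separately. On their role Section 7 says: "The two composite endpoints listed above will serve as the primary comparison of benefits and risks (pairwise comparison").

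The main benefit-risk set is ITT, up to GTED. For that period Section 2.3 says that subjects without the analysed event "will be censored on the GTED or the last contact date whichever occurs first". There is no separate rule for death, and the SAP names no competing-risk estimator.

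**The concern.** A patient who dies of heart failure can no longer have a critical-space bleed or an MI. Censoring at death lets the Kaplan-Meier estimator assume that the patient would have gone on to bleed at the same rate as the survivors. One minus Kaplan-Meier then exceeds the proportion of patients who actually have the event. Section 7 uses it as that proportion, because it multiplies it by 10,000 patients and inverts it to NNT or NNH. Mortality in this population is high, so the competing event is common.

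The bias is also uneven. Every non-bleeding death is an event in the benefit composite, so only bleeding deaths compete with it. In the risk composite every non-bleeding death is censored. The pair chosen as the primary benefit-risk comparison therefore sets a nearly unbiased estimate beside an inflated one. Non-fatal MI and non-fatal ischemic stroke, when reported singly, are inflated in the same way as bleeding.

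**Working it through.** The SAP gives no figure for these absolute risks, so there is none to reproduce. One design input can be checked. Section 1.4 puts the revised placebo rate at about 16%/year, "based on the observed combined event rate at 14%/year (assumed 20% of RRR remains"). With 1:1 allocation, 0.14 / [(1 + 0.8)/2] = 15.6%, which agrees.

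**Inputs**
- Competing mortality c, upper value 14%/year. Section 1.4: "Event rates in the placebo group for the components ACM, MI, and stroke are expected to be approximately 14%, 4%, and 2% per year".
- Lower value about 10%/year, an assumption that scales by observed combined over planned placebo event rate: 14% × 14/19 = 10.3%.
- MI 4%/year on placebo and a 20% RRR, so 3.2%/year on rivaroxaban (Section 1.4; applying the composite's RRR to MI alone is an assumption).
- Benefit composite 16 vs 12.8%/year (revised placebo rate, 20% RRR).
- Bleeding composite 0.6 (rivaroxaban) vs 0.4%/year (placebo). This is assumed, because the SAP gives no bleeding rate.
- Bleeding death 0.2 vs 0.2, or 0.2 (placebo) vs 0.3 (rivaroxaban) %/year, assumed.

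**Formulas** (constant hazards, h for the event and c for competing death)
- Kaplan-Meier risk: 1 − exp(−h t)
- Cumulative incidence: h/(h + c) × [1 − exp(−(h + c) t)]

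Example with h = 0.004, c = 0.14, t = 1: Kaplan-Meier 0.003992; cumulative incidence 0.004/0.144 × 0.13411 = 0.003725; ratio 1.072.

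**Per-arm ratio, Kaplan-Meier over cumulative incidence**

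| Event hazard | c | 1 year | 2 years | 3 years |
|---|---|---|---|---|
| 0.4%/yr (bleeding) | 10% | 1.051 | 1.103 | 1.157 |
| 0.4%/yr (bleeding) | 14% | 1.072 | 1.146 | 1.224 |
| 4%/yr (MI) | 10% | 1.051 | 1.102 | 1.154 |
| 4%/yr (MI) | 14% | 1.071 | 1.144 | 1.220 |

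The ratio hardly depends on h, so the missing bleeding rate does not matter for this step.

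**Benefit composite, between-arm difference.** The ratio is 1.001 to 1.003 over 1 to 3 years with equal bleeding death, and 0.999 to 0.995 with 0.2 vs 0.3%/year.

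**Between-arm differences per 10,000** (each range runs over c = 10 to 14%; in the reduced case mortality is c on placebo and 0.8c on rivaroxaban)

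| Quantity | Mortality | Year | Kaplan-Meier | Cumulative incidence |
|---|---|---|---|---|
| Bleeding excess | equal | 1 | 19.9 (NNH 503) | 18.6-18.9 (NNH 528-538) |
| Bleeding excess | equal | 3 | 59 | 48-51 |
| Bleeding excess | reduced 20% | 1 | 19.9 | 19.3-19.5 |
| Bleeding excess | reduced 20% | 3 | 59 | 54-56 |
| MI prevented | equal | 1 | 77 | 72-73 |
| MI prevented | equal | 3 | 215 | 177-187 |
| MI prevented | reduced 20% | 1 | 77 | 68-71 |
| MI prevented | reduced 20% | 3 | 215 | 148-165 |

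With mortality reduced, the bleeding error changes sign below a bleeding hazard ratio of about 1.22 to 1.24. At 1.1 (0.44 vs 0.40%/year) and 3 years, Kaplan-Meier gives 11.8 and cumulative incidence 13.5-14.0. More patients survive on rivaroxaban to be exposed to bleeding, and Kaplan-Meier does not count that.

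**Precision.** The standard error is √{[p₁(1−p₁) + p₀(1−p₀)]/2,500}, with 2,500 per arm. For bleeding at 1 year and c = 14%, p = 0.00558 and 0.00373, which gives 19.2 per 10,000.

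**The case against.** The strongest counter-argument is materiality. Section 7 decides on differences, not per-arm risks. For bleeding, the error in the difference may be an overstatement, a smaller one, or an understatement, depending on a mortality effect and a bleeding hazard ratio that the SAP does not give. At 1 year, the only committed horizon, the bleeding excess moves by 0.4 to 1.3 per 10,000, far below its standard error. The 2- and 3-year estimates are optional, and the plots are one of several formats to be used as appropriate. The person-year rate yields its own excess and NNT/NNH and is unaffected. Benefit-risk balance is an exploratory objective, Section 7 disclaims hypothesis testing and calls its composites a starting point, and no success claim depends on these numbers.

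The inputs can be criticized too. The 14% mortality and 4% MI rates belong to the original 19%/year design, whereas 16% is the revised rate. The 10% bound divides a both-arm observed rate by a planned placebo rate. The all-MI rate stands in for non-fatal MI.

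All of this limits the weight of the point, and most of it stands. On the inputs, scaling placebo to placebo gives 14 × 16/19 = 11.8%/year, for a per-arm overstatement of 6% at 1 year and 19% at 3, inside the stated range. None of it makes one minus Kaplan-Meier the right estimator of how many of 10,000 patients are affected. The bias does not shrink with sample size, and it grows at the horizons the SAP contemplates.

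**Conclusion.** The point holds as a minor one. Under the assumptions above, Kaplan-Meier overstates each arm's risk of the bleeding composite and of the non-fatal components by 5-7% at 1 year, 10-15% at 2 and 15-22% at 3. The benefit composite is right to within 0.5%.

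For the between-arm excess, the relative error equals the per-arm figure if mortality is equal. If mortality falls by 20%, the bleeding excess in the example is overstated by only 2-3% at 1 year and 6-9% at 3, and is understated at a low bleeding hazard ratio. The MI benefit is then overstated more: 9-13% at 1 year and 31-46% at 3. That last figure needs an optional horizon, a single component and an assumed mortality effect together.

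The primary analysis, the alpha and the sample size are not touched.

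**What to change.** In SAP Section 7, replace the Kaplan-Meier cumulative rates with Aalen-Johansen cumulative incidence, treating death outside the analysed endpoint as the competing event. Apply it at 1 year, at any 2- or 3-year horizon explored, to the NNT/NNH derived from these rates and to the pairwise plots. Keep the person-year rates as they are; Kaplan-Meier may remain as a supporting display.

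The cost is a change of wording and a standard procedure option, with no new data. The one drawback is that the curves will differ slightly from Kaplan-Meier plots elsewhere in the report, such as the bleeding plot planned in Section 6.1; a footnote can explain why.
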